12.0 Study Timelines

12.1 CET Timeline.

1. **The duration of an individual participant's participation in the study.** Participants will be in the outreach component of the study in which they may receive mailings and calls regarding tobacco treatment options up to once per quarter for up to 30 months if they continue to meet inclusion criteria for the reports that guide such outreach.

Participants who consent to the CET will be in the study for up to 8 months (up to 2 months before a target quit date and to 6 months post-quit-date).

Participants in qualitative interviews will participate in one hour-long interview (with the option to break this interview up over multiple calls if they prefer not to do it all at one call). The total duration of the interview will be about one hour.

2. **The duration anticipated to enroll all study participants.** We anticipate completing recruitment in 30 months.

3. **The estimated date for the researchers to complete this study (complete primary analyses).** We will need 1 year after completion of recruitment to complete the study (8 months to complete follow-up data collection and 4 months to complete primary analyses), and thus anticipate completing this study by mid 2027).

13.0 Procedures Involved

13.1 Study Procedures.

Tobacco treatment outreach. Patients who meet criteria for inclusion on quarterly CRDS reports will first receive a mailed letter informing them that tobacco treatments are available and that quitting smoking has important benefits during cancer care. Patients will also be informed in the letter that they will receive phone outreach from UW-CTRI regarding their tobacco treatment options over the next 12 weeks unless they prefer to opt out of such outreach by calling UW-CTRI to ask that they not receive future tobacco treatment outreach. UW-CTRI study coordinators will make up to 5 attempts to reach patients who do not opt of such calls over 12 weeks. The outreach letter and phone outreach script are uploaded with the application.

Tobacco treatment facilitation. When they reach patients on the phone, UW-CTRI study coordinators will talk with patients about the benefits and challenges of quitting smoking during cancer care and will describe available treatment options (enrolling in Wisconsin Tobacco Quit Line (or other applicable quit line) services; working with their primary or oncology care team; enrolling in the CET) and ask which, if any, treatments the patient would prefer. Patients who decline any treatment will be offered the number of the WTQL/national quit line number. A script for these treatment offers is uploaded with the application.

CET screening. Patients who express interest in the CET will be given information about screening and enrollment procedures and then asked if they assent to eligibility screening. Those who do will complete a brief eligibility screen during the same phone call. Those who do not meet eligibility criteria to continue will be offered quit line services and reminded that their care teams may be able to help them quit smoking, as well. Ineligible participants will also be asked if they would like to participate in a sub-study that involves one phone interview. Those who pass the screening will move on to the oral informed consent process.

Interviews. Up to 32 people, including those who are not eligible or do not enroll in the CET, will be offered an additional \$40 to complete a one-hour telephone interview to gather information that will help improve the way tobacco treatment is offered to people who have had cancer. Participants will first complete an oral consent procedure (uploaded with

PROTOCOL TITLE: Comparative Effectiveness Trial of Tobacco Cessation Treatments among Cancer Patients who Smoke

the application). The interview will address the participants' cancer experiences, tobacco use history, smoking and supportive care outreach, and smoking treatment. The interview outline is uploaded with the application. These interviews will be recorded and transcribed without participant identifying information.

Oral consent. In the oral consent process, UW-CTRI study coordinators will read the oral informed consent script to participants and will then ask if they have any questions. The study coordinator will answer questions during the call, or will schedule a follow-up call if the patient needs more time to make a decision about the study or if the study coordinator needs to consult with the PI or other team member to address the patient's concerns or questions. Once the patient's questions have been fully addressed, the patient will be asked questions to assess their comprehension of key CET study features. People who are unable to answer these questions correctly, even after review of key points by the study coordinator, will be considered unable to consent and will be referred to their care team and given information about WTQL services. Those who pass the comprehension screening will be asked if they consent to participate in the CET study.

Baseline assessment. Next, participants will complete a baseline assessment (see uploaded survey) of their tobacco use history, nicotine dependence, quitting motivation, quitting confidence, stress, mood, wellbeing, quality of life, support system, symptom burden, and demographics. Participants will also select a target date to quit smoking within the next 60 days at this call. These activities will occur during the enrollment phone call if participants are willing and able to stay on the call. If they are not, the UW-CTRI study coordinator will schedule this assessment call within the following 1-2 weeks.

Randomization. Participants will next be randomized to treatment. Participants will be considered fully enrolled once consented, baseline assessment is complete, and randomized. Study coordinators and participants will be informed of the randomly assigned condition after the baseline assessment is completed.

Treatment procedures. These are described in section 13.1 above.

Follow-up assessments. UW-CTRI follow-up assessors will call CET participants 12 and 26 weeks after their target quit dates to collect outcome data (see uploaded follow-up surveys) including: tobacco use; quitting motivation and confidence; stress, mood, wellbeing, quality of life, support, and symptom burden; and treatment utilization, satisfaction, and adverse events. In addition to these self-report measures, counseling utilization and medication refill data will be used to track smoking treatment adherence; EHR data on healthcare utilization and diagnoses will be extracted (with patient consent provided at enrollment); and biochemical verification of abstinence claims at the 6-months post-quit follow-up

PROTOCOL TITLE: Comparative Effectiveness Trial of Tobacco Cessation Treatments among Cancer Patients who Smoke

will be obtained via carbon monoxide breath samples and urinary cotinine samples, or mailed saliva samples (as participants are able to provide them).

13.2 CET procedure schedule.

Study Phase	Enroll- ment	Treatment/Intervention Calls								Follow Up Calls	FU Visit
Study Contact	1	2	3	4	5	6	7	8	9	10	11
Week relative to target quit day (tqd, day 0)	-8 to -3	-1	0 tqd	1	2	4	8	12	12	26	26-29
Eligibility screening	✓										
Oral informed consent & HIPAA Authorization	✓										
Clinician(s) given 5 business days to disapprove study medication; medications dispensed if not disapproved	✓										
Tobacco, alcohol, and cannabis history	✓										
Nicotine dependence	✓										
Motivation to quit	✓	✓	✓	✓					✓	✓	
Quitting confidence	✓	✓	✓	✓					✓	✓	
Stress, mood, and withdrawal		✓	✓	✓					✓	✓	
Wellbeing and quality of life	✓								✓	✓	
Social support	✓								✓	✓	
Demographics	✓										
Randomization	✓										
Welcome mailing packet with study information sheet sent	✓										
Standard care (SC) counseling (10-15 minutes)		SC	SC	SC							
Standard care nicotine patch treatment (2 weeks)			SC	SC							
Enhanced care (EC), cancer-specific counseling		EC	EC	EC	EC	EC	EC	EC			
Enhanced care varenicline treatment (12 weeks)		EC	EC	EC	EC	EC	EC	EC			

PROTOCOL TITLE: Comparative Effectiveness Trial of Tobacco Cessation Treatments among Cancer Patients who Smoke

beginning with run-in period 1 week pre-quit followed by 11 weeks at full dose post-quit, as per package insert)										
Recent tobacco, alcohol, and cannabis use								✓	✓	✓
Treatment use								✓	✓	✓
Treatment satisfaction								✓	✓	
Adverse Event Assessment (all participants will be assessed through 26 weeks post-target-quit date; those in enhanced care will have additional assessments at counseling contacts specific to that arm)		✓	✓	✓	EC	EC	EC	✓	✓	✓
Biochemical verification via CO and urine cotinine (or mailed saliva cotinine)										✓

✓ = applies to both treatment arms

SC = applies only to standard care arm

EC = applies only to enhanced care arm

13.3 Research procedures:

1. Safety monitoring and risk prevention.

To reduce risks to CET participants, we will first screen them for eligibility prior to enrollment, will ask their clinicians to review and disapprove study medications that raise safety concerns for them, and then we will monitor for adverse events at all study contacts following the initiation of smoking cessation treatments in the trial. The schedule for these activities is presented above. Please note that follow-up contacts will occur for all study participants 12 and 26 weeks after their target quit date (i.e., after the end of pharmacotherapy in both conditions, which will end 2 weeks after a target quit date in the control condition and 11 weeks after the target quit date in the enhanced care condition for varenicline). The final counseling contact in the enhanced care condition will also occur at the 12-week post-quit time point.

PROTOCOL TITLE: Comparative Effectiveness Trial of Tobacco Cessation Treatments among Cancer Patients who Smoke

For qualitative interviews, interviewers will monitor for distress or confusion during the interview and will stop the interview and address the distress or confusion, as needed.

2. Biospecimens.

The only biospecimens to be collected in the study will be collected directly from CET participants at the follow-up visit 6 months after a participant's target quit date, if the participant reported no use of tobacco products at the 26-week post-quit-date follow-up call. These participants reporting abstinence from tobacco will be asked to provide a breath sample for CO testing and a single urine sample for cotinine testing at either the UW-CTRI Madison office or at their oncology clinic (if willing to schedule this so it coincides with a clinic visit). Breath samples cannot be stored and urine samples will be tested immediately after collection and then discarded the same day. If patients are unable to travel to Madison for biochemical verification of abstinence, they will be given the option of providing a saliva sample in the mail using a kit supplied by the research team. These kits would be retained only until testing by a lab is complete and would then be destroyed.

3. Drugs.

The medications to be used in this study include transdermal nicotine patches and varenicline. Both medications are approved by the FDA for use as smoking cessation aids. No other medications or devices will be used in the research.

13.4 Data Collection.

• List of data elements.

The following data elements will be extracted from EHR data via CRDS reports. These data elements are needed to enable preparation of initial study recruitment mailings that will let patients know they have been identified for the study and that they can opt out of recruitment calls and letters.

- MRN
- Name
- Phone numbers (with preferred number flagged)
- Address
- City
- State
- ZIP code
- Communication preferences (MyChart, mail, phone)
- Tobacco use status (must be smoking currently)

PROTOCOL TITLE: Comparative Effectiveness Trial of Tobacco Cessation Treatments among Cancer Patients who Smoke

- Preferred language (must be English or missing)
 - Use of smokeless tobacco
 - Use of e-cigarettes
 - Date of birth (must be at least 18 years old)
 - Sex
 - Gender
 - Race
 - Ethnicity
 - Insurance type
 - Assigned primary care provider
 - Oncologist
 - Clinic department (where seen in the past year to achieve eligibility)
 - Cancer diagnosis (diagnosis in past 3 years that conferred eligibility)
- Additional de-identified data elements will be extracted from the EHR data and Cancer Registry for patients who were initially identified as potentially eligible for the study per EHR eligibility criteria, but excluding those who actively declined study participation. The sociodemographic and cancer diagnosis elements are needed to assess the representativeness of the recruited sample and equity in the reach of smoking treatment among eligible patients. The data regarding healthcare utilization, cancer care outcomes, and environmental exposures are needed to assess care outcomes and estimate cancer care costs (overall and between Standard and Enhanced care conditions) from participants in the CET. Specific data fields are listed in supplemental documents. These data will be extracted with identifiers only for participants who enrolled in the CET and provided informed consent for EHR data use.
- In addition, self-reported data regarding the constructs shown in the study schedule above will be collected directly from participants over the phone or at the final follow-up visit. Participant responses will be documented in REDCap.
- Completion of study counseling sessions and medication refill requests and dispensing will also be tracked in REDCap to assess treatment utilization and adherence.
- Fidelity to counseling protocols will be assessed by reviewing a subset of audio-recorded counseling sessions and coding for fidelity using a checklist.
- Qualitative interviews will be transcribed and thoroughly deidentified prior to review of transcripts for interviewer feedback and for thematic analysis.

PROTOCOL TITLE: Comparative Effectiveness Trial of Tobacco Cessation Treatments among Cancer Patients who Smoke

- **Questionnaires.**
Questionnaires to be administered as structured interviews to collect participant self-report data following the schedule shown above are uploaded with the application.
- **Source records:**
 - UW Health medical or billing records via ICTR's Clinical Research Data Service (CRDS)
 - UW Health HealthLink Records (study team will directly access) Study team members will access HealthLink directly to communicate with providers about patient medication eligibility and to document study medication dispensing in patient records for care teams).
 - Data from departmental QA or QI database
 - Data from UW Health Enterprise Data Warehouse (EDW)
 - Data from PACS (Picture Archiving and Communication System); *specify whether study will use the clinical or research instance in the Radiology Department's warehouse:*
 - Data from Center for Medicare/Medicaid Services
 - Data from publicly available datasets (e.g., U.S. census data)
 - Data from outside institutions or organizations (specify:

))
 - Other (specify: _____)

13.5 Long-term follow-up.

There are no plans for long-term follow-up.

13.6 Regulatory status of study drugs.

Both varenicline and transdermal nicotine patches are currently FDA approved for use to treat smoking and are broadly available. This use of varenicline and nicotine patches in this study is considered IND exempt under category 1 (21 CFR 312.2(b)(1)).

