Special and vulnerable populations are disproportionately affected by tobacco use and its devastating effects. As such, we will not exclude them from participation in the study if they meet all other eligibility criteria. We seek to evaluate interventions that will promote abstinence from smoking from the full range of adult smokers receiving oncology care.

Study coordinators will reach out to the PCP (if at UW Health) and UW Health oncologist of patients who consented to the CET to ask them to review the randomly assigned medication regimen, and to disapprove the medication within 5 business days if they have any concerns about study medications for their patients. Study medications will be sent to participants who have provided informed consent for CET participation only after providers have had this opportunity to review and disapprove study medications. Patients whose providers disapprove varenicline, but not patch, will receive nicotine patches (for 2 weeks in the recommended usual care control condition or for 12 weeks in the intensive treatment condition). Patients whose providers disapprove nicotine patches will receive psychosocial treatments, but no study medications.

We will not reach out to patients flagged in quarterly CRDS reports as having cognitive impairment, an active power of attorney for health care, or other active health care agent.

Vulnerable populations will not be targeted for qualitative interviews.

6.3 **Consent considerations in particular populations.** We anticipate recruiting at least some participants from the groups checked below:

- Non-English speaking participants
- Illiterate or Low Literacy participants
- Participants with visual or hearing impairments
- Status Relationship: Individuals with a status relationship with the PI or other study team members (e.g., employees, students, family members)

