- Post-quit call 4 (4 weeks after the target quit date).
- Post-quit call 5 (8 weeks after the target quit date).
- Post-quit call 6 (12 weeks after the target quit date).
- Varenicline starting 7 days before the target quit date (0.5 mg once per day for 3 days, 0.5 mg twice per day for 4 days, 1 mg twice per day for 11 weeks), as per the package insert (medication instructions for patients are uploaded with the application). Those who smoke less frequently than daily will not be eligible for varenicline.
 - If patients in high-intensity treatment are ineligible for varenicline (due to contraindications reported at initial medication screening or clinician disapproval of varenicline for the patient), patients will instead be offered 12 weeks of nicotine patch therapy for use starting on the target quit date, at the following dosing schedule:
 - For those who smoke 10 or more cigarettes per day at enrollment, 21-mg patches (week 1-8), 14-mg patches (week 9-10), 7-mg patches (week 11-12).
 - For those who smoke 5-9 cigarettes per day, 14-mg patches (week 1-10), 7-mg patches (week 11-12).
 - For those who smoke 1-4 cigarettes per day, 7-mg patches.
 - Those who smoke less frequently than daily will not be eligible for patches.
 - Those whose clinicians disapprove of nicotine patch therapy for their patients will not receive patches.
- Mailed information about smoking cessation treatments available from the Wisconsin Tobacco Quit Line (or state quit line in patient's state of residence) and SmokefreeTXT, two publicly funded, remotely delivered treatment services available to the general public. These information sheets are uploaded with the application.

11.2 Drug/Device Handling.

- Study medications (nicotine patches, varenicline) will be received at the Center for Tobacco Research and Intervention by the Study Coordinator or designees in the Madison office.
- Nicotine patches will arrive in commercially packaged boxes of 14 patches each (two weeks of 21mg, 14mg, or 7 mg patches).

PROTOCOL TITLE: Comparative Effectiveness Trial of Tobacco Cessation Treatments among Cancer Patients who Smoke

- Varenicline will arrive in commercially packaged 28-day starter packs that clearly designate when and how to start the medication run-in period (beginning 1 week before the target quit day), or 28-day continuation packs (standard commercial packaging sizes).

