17.0 Provisions to Protect the Privacy Interests of Participants

17.1 Steps to protect participants' privacy interests. If any of the following apply, check the box for convenience:

- Procedures will be performed in a private area where others cannot see the procedures being performed or overhear the conversation between subjects and researchers.
- All members of the study team are up to date on their institutional HIPAA training.
- The study is not collecting information that could pose legal or reputational risks to participants.

Almost all study activities (apart from biochemical verification visits) will occur by phone. To protect participant privacy, study coordinators will encourage participants to move to private spaces during recruitment and study calls, and will offer to reschedule calls if participants are unable to do so.

Biochemical verification tests will happen in private spaces, as well (CO tests will be conducted in private rooms and urine samples will be self-collected by participants in private restrooms, without staff observation).

17.2 Sensitive information.

The only sensitive information to be collected in the study is self-reported use of cannabis. This information is needed to assess concurrent use of cannabis that may influence smoking cessation success and to interpret carbon monoxide and cotinine tests that

PROTOCOL TITLE: Comparative Effectiveness Trial of Tobacco Cessation Treatments among Cancer Patients who Smoke

could be influenced by use of combustible cannabis (in the case of CO) and use of cannabis in tobacco leaf wrappers (in the case of CO and cotinine).

17.3 Steps to make the participants feel at ease.

Collection of sensitive information about subjects will be limited to the amount necessary to achieve the aims of the research and to interpret biochemically verified abstinence data correctly.

Participants will be informed that they have the right to decline to answer any question they prefer not to answer, without penalty or punishment, and that the study has a Certificate of Confidentiality.

17.4 Authorized access to UW Health records.

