18.0 Sharing of Results

18.1 Result sharing with participants or others.

The only results that will be shared with participants will be CO test results, as these results are available immediately upon testing. Study coordinators collecting CO samples will congratulate patients whose CO tests indicate abstinence from combustible products, and will explore sources of exposure to CO (e.g., passive smoke exposure, car exhaust, improperly vented or malfunctioning equipment) among those whose expired breath contains more than 5 parts per million CO. Urine cotinine and salivary cotinine testing results will not be

PROTOCOL TITLE: Comparative Effectiveness Trial of Tobacco Cessation Treatments among Cancer Patients who Smoke

available immediately (urine testing takes at least 15 minutes, saliva samples need to be shipped for testing). These results will not be captured in participants' health records, as they capture abstinence at a particular time (in the past 1-2 days for CO, and in the past 1-2 weeks for cotinine), and should not be used to influence ongoing healthcare.

18.2 Plans to share study results with the public.

Aggregate results from this research will be shared with the scientific community and our research collaborators. The findings from this research will also be shared upon request with study participants.

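### In-person verification of week-26 abstinence falls to a role that is told the assigned arm, and no section masks whoever collects, reads or classifies the result

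*Combined protocol and SAP*

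**What the plan says.** **Who knows the arm.** Section 13.1 (Randomization) states: "Study coordinators and participants will be informed of the randomly assigned condition after the baseline assessment is completed". Other duties keep the role close to the allocation. In section 6.2 coordinators contact the participant's clinicians "to ask them to review the randomly assigned medication regimen". In section 11.2 study medication "will be received at the Center for Tobacco Research and Intervention by the Study Coordinator or designees in the Madison office".

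**Who handles the breath test.** Section 18.1: "Study coordinators collecting CO samples will congratulate patients whose CO tests indicate abstinence from combustible products, and will explore sources of exposure to CO". The exploration applies to readings above 5 ppm. This is the only CO figure in the protocol, and it stands under sharing of results, not in an endpoint definition.

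**What the test decides.** The primary effectiveness endpoint (section 3.4) is 7-day point-prevalence abstinence at 26 weeks, confirmed by CO and/or cotinine. In-person participants give both breath and urine (section 13.3). Under section 20.6, anyone without both a report of abstinence and biochemical evidence of it is coded as smoking.

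**Interpretation.** Section 17.2 explains that cannabis use is recorded because it can affect CO and cotinine results. Section 17.3 limits sensitive questions to what is needed for the aims and "to interpret biochemically verified abstinence data correctly".

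**A separate role.** Section 13.1 (Follow-up assessments): "UW-CTRI follow-up assessors will call CET participants 12 and 26 weeks after their target quit dates to collect outcome data". In-person sample collection is not assigned to these assessors, and nothing says whether they know the arm.

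**The mailed route.** Sections 16.2 and 16.5 send saliva to an outside laboratory under a separate sample code.

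**The concern.** The trial is open-label and enhanced care is the predicted winner. The plan expects some test results to need interpretation, but does not say who interprets them, by what rule, or whether that person knows the arm. The one role that the protocol links to the breath test is also the role that it says is told the arm.

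If an elevated CO were explained away more readily in one arm, the primary outcome would change for that participant, because section 20.6 leaves only two codes: verified abstinent or smoking. Section 20.2 intends the pilot estimate to guide a full-scale trial, so any distortion would carry into that trial's design. A wide pilot confidence interval does not cover this, because it describes random error and not a directional one.

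**Working it through.** **Step 1. Trace each route to a verified outcome.**

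- *Breath CO, in person.* Collected by study coordinators (18.1), a role told the arm (13.1). The reading comes from an instrument. The handling of a reading above 5 ppm for the endpoint is not stated.
- *Urine cotinine, in person.* Tested on site the same day (13.3). The person who reads it is not named, and no cutoff is given.
- *Saliva cotinine, by mail.* Assayed outside under a code (16.5), so the assay is in effect masked.
- *Discordant results.* Section 3.4 allows CO and/or cotinine. No section says what happens when breath and urine disagree, or whether a CO explained by passive smoke or cannabis counts as verified.

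No section provides masking for anyone at these steps. The protected part is the saliva assay.

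**Step 2. Would moving the test to the follow-up assessors be enough?** Not by itself. Their calls at weeks 12 and 26 also cover treatment use, satisfaction and adverse events (13.1). Adverse events are collected at every contact from 2 through 11, which includes the final visit (23.1), and the schedule in 13.2 appears to place treatment use at that visit too. An assessor who asks these items at week 12 may know the arm before week 26.

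**Step 3. How much can one classification matter?** The plan gives no expected abstinence rates for this trial, and its sample size rests on no power calculation, so there is no plan figure to reproduce. The counts below are assumed.

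Inputs: 25 per arm (4.3) and a predicted odds ratio of at least 1.50 (20.1). With *a* verified abstinent in enhanced care and *b* in standard care:

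OR = [a/(25 − a)] / [b/(25 − b)]

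| Enhanced v standard | Calculation | OR |
|---|---|---|
| 6 v 5 | (6/19)/(5/20) | 1.26 |
| 7 v 5 | (7/18)/(5/20) | 1.56 |
| 8 v 5 | (8/17)/(5/20) | 1.88 |
| 9 v 5 | (9/16)/(5/20) | 2.25 |
| 4 v 3 | (4/21)/(3/22) | 1.40 |
| 5 v 3 | (5/20)/(3/22) | 1.83 |

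The 9 v 5 row (36% v 20%) is close to the 34.5% v 21.5% that section 2.5 cites from the cancer counselling trial. Exploring other CO sources can only excuse an elevated reading, so the relevant shift adds one verified case. In enhanced care, 6 v 5 becoming 7 v 5 moves the OR from 1.26 to 1.56, and 4 v 3 becoming 5 v 3 moves it from 1.40 to 1.83. Both cross 1.50.

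The Wald 95% interval for 7 v 5 is 0.42 to 5.78 and for 6 v 5 is 0.33 to 4.84. Random error is far larger than the shift. The shift matters because it would have a direction.

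**The case against.** **CO is an instrument reading, and section 18.1 is about what participants are told.** This stands in part. A reader might infer that coordinators recode an explained reading as abstinent. No section says so, and none says who classifies. What remains is that the plan expects interpretation and leaves both the rule and the person unspecified.

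**Not all verification is open.** A reader might infer that abstinence as a whole is verified unmasked. That is too broad: the saliva assay is coded, and in-person participants also give urine.

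**Same role is not same person.** This stands. The documents do not show that whoever takes a given sample knows that participant's arm. They also do not prevent it.

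**No text suggests unequal pursuit of samples.** This stands. A reader might infer from section 20.6 that staff could press harder for samples in one arm, but no section says who schedules or chases them. The $75 payment (7.5) and the week 26 to 29 window (13.2) are common to both arms.

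**Any changed outcome at this sample size moves the OR, and 1.50 is a prediction, not a decision threshold.** Both parts are true. The table shows sensitivity to one classification and does not estimate bias.

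**Other analyses give a partial check.** Section 20.2 also lists self-reported abstinence at 3 and 6 months, which does not depend on the breath test. The sensitivity analyses in section 20.6 vary the status of people without verified abstinence. They would not reveal a difference between arms in how results came to be counted as verified.

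**Conclusion.** The plan leaves in-person verification of its primary effectiveness endpoint open to staff who know the arm, and leaves the interpretation of elevated or discordant results without a stated rule or a masked decision-maker. This is an overlap of roles and an omission. The documents do not show that bias occurs, and they give no basis for its size.

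At 25 per arm, one reclassified participant is enough to move an illustrative odds ratio across 1.50. That statement rests on assumed counts and an assumed misclassification.

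Masking would help only in part. Participants know their arm, and the endpoint starts from their own report. The change is still worth making because it is cheap and bears on the estimate that the pilot is meant to pass on. No sample-size figure changes.

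**What to change.** 1. In sections 13.1 and 18.1, state that the week-26 request for samples, and the collection and reading of CO and urine, are done by existing follow-up staff who are not told the arm.
2. At the week-12 and week-26 calls and the final visit, have these staff complete the tobacco-use items, and the test where there is one, before any treatment-use, satisfaction or adverse-event item. Alternatively, have someone else ask those items. Where an assessor has learned the arm at week 12, use another existing assessor at week 26 if one is available.
3. Classify every elevated, discordant, or cannabis- or passive-smoke-explained result from a record with the arm removed, under one rule fixed in advance and applied to both arms. Section 20.6 could hold that rule.

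The cost is some scheduling effort, a check of the item order in the follow-up surveys, and occasional accidental unmasking by participants. No new test is needed. The documents do not say how many assessors there are, so the study team should confirm that the swap in item 2 is practicable.
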